1. Participants will complete online measures at the following times:
 - a. Turning on the stimulator
 - i. Tic intensity
 - ii. Tic frequency
 - b. Turning off the stimulator
 - i. Tic intensity
 - ii. Tic frequency
 - iii. Discomfort from stimulation
 - iv. Overall symptom improvement

Texts will be sent twice daily at predetermined times, and the participant will respond with times “c.” or “d.” below depending on stimulator use when the text is received:

- c. Answering a text, stimulator currently on
 - i. Tic intensity
 - ii. Tic frequency
 - iii. Discomfort from stimulation
 - iv. Overall symptom improvement
 - d. Answering a text, stimulator currently off
 - i. Tic intensity
 - ii. Tic frequency
2. Participants may be contacted throughout the study for reminders regarding compliance or assistance in troubleshooting issues with the device or surveys.

Online at conclusion of study

1. The study concludes 4 weeks (± 5 days) after the initial visit (or earlier, if the participant decides to stop treatment before 4 weeks).
2. We review the online questionnaires and collect the following additional measures:
 - a. Current symptom status
 - i. Adult Tic Questionnaire (ATQ) tic rating
 - ii. Premonitory Urge for Tics Scale (PUTS) [10]
 - b. Treatment efficacy and side effects
 - i. [Modified Clinical Global Impression – Efficacy Index](#)
 - ii. Patient perception of duration of improvement after stimulation
 - iii. Patient’s plans to continue using device
 - c. Open-ended comments
 - i. On device
 - ii. On study

Subject Payments

Participants will be given the TENS unit to keep at the successful conclusion of the study, a value of approximately \$30, to compensate for their loss of time.

Clinical vs. research purposes

The actual treatment with MNS is for clinical purposes and will be controlled by the participant. All other procedures in this study are done for research purposes.

POTENTIAL RISKS

(The language below, in this section, is addressed to the patient, as in an informed consent document.)

You may experience one or more of the risks indicated below from being in this study. In addition to these, there may be other unknown risks, or risks that we did not anticipate, associated with being in this study. You will be told of any new information that may affect your willingness to participate in this study. [name] will answer any questions you have about these risks.

MNS

Likely:

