- Discomfort in the forearm, wrist or hand during active stimulation
- Mild skin irritation from applying or removing the surface electrodes

Other study procedures

Likely:

- The questionnaires may be slightly boring, fatiguing or challenging.

Rare:

- Some participants may be sensitive to components of the electrode pads and develop a rash where the pads are affixed to the skin. If this happens, stop using the device and contact us.
- The questions that you are asked during this study could make you feel uncomfortable. If any question makes you feel uncomfortable, you may choose not to answer it.
- Confidential information about you may be accidentally disclosed. However, we think the risk of accidental disclosure is small. The information we gather during the course of the study is coded only by a study number and is kept separately from your name, address, etc. The exception is that your phone number will be shared with Twilio.com, the text services provider we contract with.

LOCATIONS / SITES OF STUDY

Data collection: Washington University in St. Louis, and participant's location when answering surveys

Data analysis: Washington University in St. Louis

STUDY DURATION

Anticipated duration of entire research activity per participant:

- 4 weeks

Anticipated duration of entire research activity:

One year

SAMPLE SIZE

N = 38 (study completers of the “Peripheral induction of inhibitory brain circuits to treat Tourette’s: pilot” study, which was powered to have 32 study completers with up to 38 participants screened)

Power considerations

As this study is an exploratory study to determine the viability of this type of therapy in the real world setting, the sample size was chosen for convenience to include only completers of the MNS pilot study. However, a sample size of 32 provides 75% power to detect improvement of -25% in tic severity or frequency ratings (one tailed). A change of -25% in YGTSS total tic scores is considered clinically meaningful [17].

INCLUSION CRITERIA

Inclusion criteria for all participants:

- Completed participation in the study called “Peripheral induction of inhibitory brain circuits to treat Tourette’s: pilot”
- Informed consent by adult participant; assent by child and informed consent by guardian

EXCLUSION CRITERIA

Exclusion criteria for all subjects:

- Has an implanted device that could be affected by electrical current
- Pregnancy known to participant or (for children) to the parent

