- Severe or unstable systemic illness
- Factors (such as exaggerated symptom report) that in the judgment of the principal investigator may make the outcome measures inaccurate
- Judged by investigator to be unlikely to complete study procedures

Additional exclusion criteria were required for participation in the RCT.

CONCOMITANT MEDICATIONS

Required: none

PROHIBITED MEDICATIONS

none

TREATMENTS AND DOSAGE

TENS stimulation

- The device (TENS-7000) was judged by the FDA to be substantially equivalent to similar approved devices in the “Transcutaneous electrical nerve stimulator for pain relief” category, 501(k) premarket notification number [K080661](#).
- 12 Hz square-wave, 200 μ s pulses will be delivered over the median nerve at the wrist at the threshold for thumb movement to surface electrodes (conductive gel, 30 mm apart center-to-center, anode distal).
- The participant will determine the current delivered, using an analog knob on the TENS unit. We instruct them that we believe the stimulation has to cause thumb movement in order to be effective (based on the Nottingham EEG results), so they will likely need to adjust the current delivered each time they turn it on, given expected fluctuations in actual current delivery with changes in electrode position or electrode-skin resistance throughout the day.
- Participant can choose right or left median nerve (we will suggest their nondominant hand to minimize interference with daily activities).
- Participant will determine duration and timing of stimulation.

ANALYSIS PLAN/APPROACH/METHODOLOGY

Outcome measures

The primary outcome measures are derived from the surveys administered online throughout the study period. Surveys completed when the stimulator is turned on will assess the tic frequency and intensity prior to stimulation. For surveys where the stimulator is currently on or was recently turned off, the tic frequency and intensity will be reported in addition to discomfort and overall symptom relief. The time of each survey will be recorded in order to determine how long the device was on and the relative timing of each survey. Analysis can begin for each participant after their final survey has been completed.

Primary Outcome Measures:

1. Time spent using the device (minutes per day and number of days per week used over four-week period)
2. Do you expect to continue to use the stimulator? (yes/no/maybe, at study conclusion)

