3. Comparison of tic frequency between “turning ON” and “turning OFF” surveys (scale of 0-5)
4. Comparison of tic intensity between “turning ON” and “turning OFF” surveys (scale of 0-5)
5. Mean discomfort while using stimulator (scale of 0-3 adapted from the CGI-I Efficacy Index)
6. Relationship to blinded study results (correlation of change in tic frequency and intensity during this study as in outcome measures 3 and 4 above with change in tic frequency and intensity respectively during active, rhythmic stimulation during the RCT).

Secondary Outcome Measures:

1. What was the overall impact of the stimulation on symptoms throughout the study period? (CGI-Efficacy index)
2. How much discomfort did the stimulation cause throughout the study period? (CGI-Efficacy index)
3. Average therapeutic effect while using stimulator
4. Comparison of tic severity prior to and at the end of the study

5. Check whether reported symptom improvement across different stimulation sessions was influenced by stimulation intensity or reported discomfort
6. Comparison of tic frequency between “more than 60 minutes after turning off stimulator” and “less than 60 minutes after turning off stimulator”
7. Comparison of tic intensity between “more than 60 minutes after turning off stimulator” and “less than 60 minutes after turning off stimulator”
8. “How long do you think the improvement in your tics lasted after you turned off the device?”
9. Compare participants’ perception of tic improvement from post-study survey to their results collected during the study
10. Compare participants’ perception of length of tic improvement after turning off the stimulator from post-study survey to their results collected during the study
11. Do certain participant characteristics predict who will be “responders”?
12. Qualitative analysis of open-ended questions

Data analysis

Data storage, sharing and management. Survey data, which **will not contain PHI**, will be collected and stored on Google Forms. This data will be shared on the [Open Science Framework](#).

Overall statistical approach. To prevent “HARKing” (hypothesizing after results are known) [20], we have **registered our hypotheses** and analysis strategy on [OSF.io](#) prior to initiating enrollment. For this pilot study, all statistical tests will be reported independently, with a warning about multiplicity of tests. However, we limit the number of primary outcome measures.

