Aim 1 (determining real-world utility of stimulation). Descriptive data regarding the duration of use of the device will be reported as the mean and standard deviation of minutes per day, as well as the mean number of days used per participant. Answers to the question, “if you had a free stimulator, would you continue to use it after the study finishes?” will be reported as percentages answering “yes,” “no,” and “maybe.” Additionally, a summary of common themes to the open-ended questions about the device will be reported.

Aim 2 (determining momentary self-rated efficacy and side effects of stimulation). Comparisons of tic frequency and intensity ratings immediately prior to and following use of the simulator will be reported as paired t-tests. A similar analysis will be completed for ratings of frequency and intensity made less than 60 minutes after turning off the stimulator vs. more than 60 minutes after turning off the stimulator (unpaired t tests). Average discomfort and average therapeutic effect while using the stimulator will be reported descriptively as percentage of participants choosing each rating. A similar analysis will be conducted on average discomfort and average therapeutic effect over the entire study period as reported in the final survey. Additionally, the discomfort and therapeutic ratings collected throughout the study will be compared with those taken at the end of the study. Participants’ scores on the ATQ (adult tic questionnaire) and PUTS scale (premonitory urge for tic scale) before and after the study will be compared using the paired t-test. Participants’ responses to the question “How long do you think the improvement in your tics lasted after you turned off the device?” will be reported as percent of participants choosing each option, and these perceptions will be compared with their numerical ratings throughout the study. Finally, we will determine if certain factors have a significant impact on who is a “responder” to the device, as measured by those participants with a greater than 25% reduction in tic frequency or intensity during stimulation. The factors to be examined include

age, sex, baseline YGTSS, complex tics ever, phonic tics ever, baseline ADHD severity, and baseline OCD severity.

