Aim 3 (Compare results of trial with those from “Peripheral induction of inhibitory brain circuits to treat Tourette’s: pilot”). Both changes in tic frequency and tic intensity will be compared between the RCT and the open-label study using correlation analysis. The change observed in the RCT will be plotted on the x-axis, and the change observed in the open-label study will be plotted on the y-axis. A line of best fit will be generated to determine if there is a significant relationship between the two, and if so, in what direction it occurs.

Additional analysis details. Outliers will be determined at the level of the individual variables before the main analyses. If the distribution clearly deviates from a normal distribution on visual inspection because of outlying values, after transformation if appropriate, we will use a nonparametric analysis.

SAFETY MONITORING

We anticipate no adverse events other than possible mild, transient discomfort related to the stimulation. However, we will report any adverse events to the Institutional Review Board according to its regulations, including an annual summary.

No serious adverse events (SAEs) are expected. The PI will monitor for unanticipated problems, life-threatening events or deaths. If contrary to expectations any SAE occurs that the investigator considers possibly, probably or definitely related to participation in the study, we will confer with the IRB before continuing enrollment.

REFERENCES CITED

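### Home-use discomfort is planned to be summarised descriptively only as an average, so the report would not show how often high discomfort occurred

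*Combined protocol and SAP*

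**What the plan says.** Under 'Online during study period', discomfort ("iii. Discomfort from stimulation") is asked at each switch-off and at each text answered with the stimulator on. "Texts will be sent twice daily at predetermined times", and the number of sessions is left open: under 'Treatments and dosage', "Participant will determine duration and timing of stimulation".

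Two places say how these ratings will be summarised:

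- Primary outcome 5: "Mean discomfort while using stimulator (scale of 0-3 adapted from the CGI-I Efficacy Index").
- Data analysis, Aim 2: "Average discomfort and average therapeutic effect while using the stimulator will be reported descriptively as percentage of participants choosing each rating".

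Discomfort also appears in these places:

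- Secondary outcome 2 is a single overall discomfort rating at the end of the study.
- Secondary outcome 5 asks whether discomfort in a session influenced the improvement reported.
- The Aim 2 paragraph says the ratings made during the study will be compared with the final ones, without giving a method.

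On harm, 'Potential risks' lists "Discomfort in the forearm, wrist or hand during active stimulation" first of two likely effects of stimulation. 'Safety monitoring' states: "We anticipate no adverse events other than possible mild, transient discomfort related to the stimulation".

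**The concern.** Aim 2 sets out to determine momentary side effects, and the study is meant to inform a later controlled trial of a portable device. Discomfort is the only side effect that the repeated surveys rate. For tolerability, a reader wants to know how bad it got and how often, as well as the typical level. A four-week average answers only the last of these.

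The Aim 2 sentence is also unclear. A participant chooses a rating at each survey but does not choose an average, and no rule turns a mean such as 1.4 into one of the four categories. Two analysts could produce different tables from the same data.

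At stake is the tolerability statement. A low average would look consistent with the expectation of mild, transient discomfort whether or not some sessions were rated at the top of the scale.

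**Working it through.** **Inputs from the documents.** The scale is 0 to 3 (primary outcome 5). There are two texts a day for four weeks, so at most 2 × 28 = 56 text ratings, with discomfort asked only if the device is on. There is one further rating per switch-off, and the number of sessions is not fixed. The documents state no discomfort figure, so there is nothing to reproduce.

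**Assumed.** The number of ratings per participant (14, 28 or 56) and, in step 3, every rate.

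**1. What an average can hide.** With m ratings, k of them 3 and the rest 0, the mean is 3k/m.

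| m | k | Mean |
|---|---|---|
| 14 | 2 | 6/14 = 0.43 |
| 14 | 6 | 18/14 = 1.29 |
| 28 | 4 | 12/28 = 0.43 |
| 28 | 13 | 39/28 = 1.39 |
| 56 | 9 | 27/56 = 0.48 |

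If means were rounded to the nearest category (an assumption, since the plan gives no rule), the rows with k = 2, 4 and 9 would be counted at 0 and the other two at 1.

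**2. A less extreme background.** If the other ratings are 1 rather than 0, the mean is (3k + (m − k))/m. With m = 28 and k = 6 this is (18 + 22)/28 = 1.43, which still rounds to 1.

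**3. Illustration across participants.** Suppose a person's probability of a top rating follows Beta(1, b), with b = (1 − p)/p and average p. The chance of at least one top rating in m is then m/(b + m).

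| p | b | m = 14 | m = 28 |
|---|---|---|---|
| 0.03 | 32.33 | 14/46.33 = 30% | 28/60.33 = 46% |
| 0.05 | 19 | 14/33 = 42% | 28/47 = 60% |
| 0.10 | 9 | 14/23 = 61% | 28/37 = 76% |

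With the remaining ratings simulated at 0/1/2 with probabilities 0.55/0.35/0.10, between 93% and nearly 100% of participants who gave any top rating had a mean below 1.5. Only 2% to 6% of them had a mean below 0.5, and about 1% or fewer of those with two or more top ratings did. The background mean alone is 0.35 + 2 × 0.10 = 0.55.

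**4. Sensitivity to the assumptions.** With the same p for everyone and independent ratings, the chance of any top rating is 1 − (1 − p)^m. It runs from 25% (p = 0.02, m = 14) to 99.7% (p = 0.10, m = 56). A range this wide shows that the size cannot be fixed from the documents.

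**5. Do other analyses recover the information?** Secondary outcome 2 is one recalled global rating per person, with no count of bad sessions. Secondary outcome 5 uses discomfort to explain improvement. The comparison with the final survey has no stated summary. Adverse events go to the IRB, but nothing says how a high survey rating relates to an adverse event. None of these reports how often high ratings occurred.

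**The case against.** The case on the other side has real force.

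- **The category counts rest on a rule the plan does not contain.** Unrounded, the participant with four 3s shows 0.43, which is not zero. This stands, and the missing rule is part of the point.
- **The Aim 2 sentence might mean a distribution of the ratings themselves.** This is possible, but the unit is participants, the quantity is called an average and primary outcome 5 is a mean, so one average per participant is the likelier reading.
- **Between-session variation is not established.** The plan says "they will likely need to adjust the current delivered each time they turn it on". That could mean discomfort varies, but readjusting to the same thumb-movement threshold could equally steady it. The text does not settle this.
- **There are other routes.** The final-survey rating is one value per person, so a top overall rating would be visible there. Open-ended comments will be summarised, and the survey data will be shared publicly. These soften the problem without committing the study to report the frequency of high discomfort.
- **The study is exploratory, with a convenience sample and a non-significant-risk device.** This limits the weight of the point, but the remedy is correspondingly small.

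A reader might infer that people with several top ratings would be reported as having no discomfort. The documents do not support that: they print no anchors for the adapted scale, and in step 3 a mean below 0.5 after several top ratings is rare. A reader might also infer that the plan cannot reveal anything beyond mild discomfort. That goes too far, given the ambiguous wording and the separate final rating.

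**Conclusion.** The point holds as an incomplete description of a harm. The only descriptive summary planned for the home-use discomfort ratings is a mean or average, and the step from repeated ratings to percentages of participants is undefined. Read as one average per participant, the summary largely hides occasional top ratings: 4 of 28 give 0.43 and 13 of 28 give 1.39 when the rest are 0.

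That arithmetic needs only the 0-3 scale and an assumed number of ratings. The shares of participants in steps 3 and 4 depend on assumed rates and are illustrations. Whether this study would in fact under-report discomfort, and by how much, is unknown. This is a worthwhile, inexpensive improvement. It does not invalidate primary outcome 5.

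**What to change.** Keep mean discomfort as primary outcome 5. In the Aim 2 paragraph, state how each participant's ratings are reduced to the value that is tabulated, and add wording such as:

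> For each participant, the worst discomfort rating (0-3) across all turning-OFF and stimulator-on text surveys will be derived, and the number and percentage of participants at each worst rating reported. The percentage of each participant's ratings that were 2 or 3 will be summarised as median and range.

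Cite these figures beside the mean in any statement about tolerability.

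The cost is a few sentences and one table, from ratings already collected; no visits, surveys or staff are added. The downside is that the worst rating tends to rise with the number of ratings, which depends on how much each participant chooses to use the device. It must therefore be read together with the percentage of ratings at 2 or 3. The change concerns reporting only and alters no treatment setting or clinical rule.

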Here we propose (a) to determine the real-world usage and apparent utility of stimulation in people with chronic tics, and (b) to determine momentary self-rated efficacy and side effects of stimulation. In addition, we will compare results from this study to those from the "Peripheral induction of inhibitory brain circuits to treat Tourette's: pilot" study, from which participants will be drawn, in order to compare laboratory and real-world efficacy.

Aim 1. Determine the real-world usage and apparent utility of stimulation in people with chronic tics. Participants will be allowed to choose when and for how long to use the stimulation, thus reflecting how patients would use the stimulation in their daily lives outside of a research study.

Aim 2. Determine momentary self-rated efficacy and side effects of stimulation, using surveys taken at the beginning and end of stimulation periods, as well as twice daily when prompted.

Aim 3. Compare results of this trial with those from "Peripheral induction of inhibitory brain

circuits to treat Tourette's: pilot." Participants in this study are drawn from completers of the "peripheral induction" blinded RCT, allowing for clear comparisons between the laboratory conditions of the first study and the real-world conditions of the second.

Completion of these Aims will provide practical information that can inform a future, controlled clinical trial of chronic MNS delivered by a portable device.

STUDY DESIGN

Overall study timeline

The study will complete enrollment within 11 months and complete all human subjects procedures within 1 year.

Overview of each subject's participation

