First we screen potential participants to ensure they meet criteria for study enrollment. All participants will be drawn from completers of the study "Peripheral induction of inhibitory brain circuits to treat Tourette's: pilot," and we will draw much of the demographic and clinical information from the RCT. Participants will attend one session (whenever possible, in person at the same visit as the final study visit for the RCT), in which they will learn how to use the device and have it set to appropriate settings. They will then take the device home to use for four weeks, during which time they will fill out brief surveys whenever they turn the device on and off, as well as at two other points throughout the day. These surveys record tic intensity and frequency, as well as discomfort due to the device. Participants will also complete a more extensive survey at the conclusion of the study.

Recruitment

Participants will be recruited from completers of the study "Peripheral induction of inhibitory brain circuits to treat Tourette's: pilot."

First visit

1. We present an informed consent document to participants (to parents of potential child participants) explaining the study, risks and benefits of participation and that participation is voluntary. The ICD will be provided online prior to the initial visit. Potential subjects will review the informed consent document with the investigator or designee and will have opportunity to resolve questions or concerns. Adult participants will provide their own informed consent. For child participants, consent from one parent or guardian is sufficient, as the study is minimal risk. Children must assent to participate.
2. All data from the "Peripheral induction of inhibitory brain circuits to treat Tourette's: pilot" study will be imported for comparison with information collected during this study.
3. If more than 2 weeks have elapsed since the most recent administration of the Adult Tic Questionnaire (ATQ) [8,9], participants will be asked to repeat it.
4. Explain use of the TENS unit, including which settings may be changed by the participant and which settings should remain on the settings established by the investigator.

5. Attach electrodes.
6. Determine stimulation threshold (12 Hz, pulse width 200μs), starting at 0 and increasing slowly until a twitch of the thumb is seen.
7. Verify that the participant is able to set up and turn on the device on their own.

Online during study period

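### Skin irritation is listed as a likely risk, but discomfort is the only side effect the plan names for measurement, so skin reactions would be counted only when volunteered

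*Combined protocol and SAP*

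**What the plan says.** Aim 2 (Objectives) reads "Determine momentary self-rated efficacy and side effects of stimulation, using surveys taken at the beginning and end of stimulation periods", with twice-daily prompted surveys in addition.

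Potential Risks puts two separate items under MNS, Likely. One is discomfort of the arm or hand while the current is on. The other is "Mild skin irritation from applying or removing the surface electrodes". Under Other study procedures, Rare, it adds that some participants may react to the pads and "develop a rash where the pads are affixed to the skin"; they are asked to contact the team if so.

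The overview of each subject's participation describes the home surveys thus: "These surveys record tic intensity and frequency, as well as discomfort due to the device". In the itemised list (Online during study period), the side-effect entry is "Discomfort from stimulation". It is asked at switch-off and at a text answered with the stimulator on, but not at switch-on or at a text answered with it off.

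The final survey (Online at conclusion of study) has a block headed "Treatment efficacy and side effects". It contains a modified CGI Efficacy Index, given as a link, and questions on duration of benefit and plans to continue. Open-ended comments on the device and the study follow.

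Safety Monitoring states "We anticipate no adverse events other than possible mild, transient discomfort related to the stimulation". It then undertakes to report any adverse events to the IRB, with an annual summary.

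**The concern.** The protocol treats skin irritation and stimulation discomfort as different risks and calls both likely, but it plans to measure only one. A discomfort rating cannot separate the two. It is also asked only during or just after stimulation, whereas irritation is said to come from applying or removing electrodes.

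The study is meant to inform a later controlled trial of chronic stimulation with a portable device. Skin tolerability over four weeks of self-directed home use is something that trial would want to know, and analysts cannot recover afterwards what was never asked. If few skin complaints appear in the results, a reader could not tell whether few occurred or few were mentioned.

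The Safety Monitoring sentence adds a wording conflict, because it expects less than the risk list in the same document.

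**Working it through.** The plan states no figure on this point, so there is nothing to reproduce. The check sets the listed risks beside everything the plan says it will measure.

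**Step 1. Risk against measurement**

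| Place | Discomfort | Skin irritation or rash |
|---|---|---|
| Potential Risks | Likely | Irritation likely; pad rash rare |
| Surveys at switch-off, and at texts with stimulator on | Asked | Not listed |
| Surveys at switch-on, and at texts with stimulator off | Not listed | Not listed |
| Final survey, Efficacy Index | Named as its use in secondary outcome 2 | Form not reproduced; no such use named |
| Primary outcomes | No. 5 | None |
| Secondary outcomes | Nos. 2 and 5 | None by name; no. 12 analyses free text |
| Data analysis, Aim 2 | Distribution of ratings, in-study and final, and their comparison | None |
| Safety Monitoring | Anticipated | Not anticipated; any adverse event goes to the IRB |

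**Step 2. Routes by which a skin reaction could still be known**

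- Open-ended device comments. Data analysis, Aim 1, summarises these by recurring theme, not by count.
- Contact initiated by the participant. The instruction is attached to pad rash, not to the milder irritation listed as likely.
- Adverse-event reports to the IRB. No method of asking participants about events is given.

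None of these puts a skin question to every participant.

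**Step 3. What a volunteered count can show (illustration)**

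Inputs from Sample Size: N = 32 completers, up to 38. Assumed, because the documents give no rates: true proportion affected p = 10%, 25% or 50%; chance that an affected participant mentions it s = 25% or 50%.

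Expected reports = N × p × s. Chance of no report = (1 − p × s)^N.

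For N = 32, p = 10%:

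- s = 25%: 32 × 0.10 × 0.25 = 0.8 reports; (1 − 0.025)^32 = 44.5% chance of none
- s = 50%: 32 × 0.10 × 0.50 = 1.6 reports; (1 − 0.05)^32 = 19.4% chance of none

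| N | p | Affected (N × p) | Expected reports, s = 25% to 50% | Chance of none, s = 25% to 50% |
|---|---|---|---|---|
| 32 | 10% | 3.2 | 0.8 to 1.6 | 44.5% to 19.4% |
| 32 | 25% | 8 | 2 to 4 | 12.7% to 1.4% |
| 32 | 50% | 16 | 4 to 8 | 1.4% to below 0.1% |
| 38 | 10% | 3.8 | 1.0 to 1.9 | 38.2% to 14.2% |
| 38 | 25% | 9.5 | 2.4 to 4.8 | 8.6% to 0.6% |
| 38 | 50% | 19 | 4.8 to 9.5 | 0.6% to below 0.1% |

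The count depends on p and s only through their product. With N = 32, four reports are expected both at p = 25%, s = 50% (32 × 0.25 × 0.50) and at p = 50%, s = 25% (32 × 0.50 × 0.25). The data cannot tell these apart.

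**Step 4. What a direct question would give**

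If every participant answers, s no longer depends on volunteering and n/N estimates the self-reported rate. Exact (Clopper-Pearson) 95% intervals would be 11.5% to 43.4% for 8/32, 31.9% to 68.1% for 16/32, 13.4% to 43.1% for 10/38 and 33.4% to 66.6% for 19/38. These are wide, but they are interpretable.

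**The case against.** The strongest reply is that the study already has proportionate means of hearing about skin problems. It is exploratory and minimal-risk, with an FDA-cleared device. It collects free text on the device, lists qualitative analysis of that text as a secondary outcome, invites contact about a rash, and reports any adverse event. A reader might infer that skin reactions cannot be reported at all. That does not follow, because a count of volunteered cases is possible. What is missing is systematic asking.

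A reader might also infer that Aim 2 goes unmet. The aim speaks of momentary effects of stimulation, while the irritation is attributed to handling the electrodes, so it can be argued to fall outside the aim. The protocol does file it under MNS risks, but an unmet aim is one reading and is not demonstrated.

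Nor can it be said that the Efficacy Index omits skin effects. The modified form is linked and not reproduced, and it sits in a block that mentions side effects. All that can be said is that the outcome list describes its side-effect use only as discomfort.

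Finally, the risk section is written in consent-form language, which tends to be inclusive, and the Safety Monitoring mismatch is mild. That stands, but the two passages still disagree as written.

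**Conclusion.** The gap is real and minor. Discomfort is the only side effect the plan names for measurement. Skin reactions, which the same plan calls likely, would be known only from volunteered reports. Any such number is a lower bound, probably an under-count, and should not be presented as a frequency. The Safety Monitoring sentence also does not match the risk list.

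The size of the under-count cannot be taken from the documents. The figures above rest on assumed rates and an assumed 25% to 50% chance of mention, and they assume participants report independently. The conclusion about ascertainment does not depend on those values, only on some affected participants saying nothing unless asked. It would fall away if the linked Efficacy Index form turned out to contain a skin item. No efficacy outcome or analysis is affected.

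**What to change.** - Add one yes/no item with a text box to the existing final survey, for example: any skin irritation, rash or other problem from the electrodes or stimulation?
- Under Data analysis, Aim 2, state that the result will be reported as n/N answering, with an exact 95% confidence interval, and that free-text or spontaneous reports will be shown separately as volunteered.
- Reconcile the Safety Monitoring sentence with the Potential Risks list so that the two passages agree.

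The cost is one survey item, a sentence or two of text, a few seconds per participant and one more descriptive result. A repeated in-study item is optional; given the existing survey load, the final-survey item is enough to close the gap.
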